14. ETHICS AND RESPONSIBILITIES

Although disease progression of MacTel appears to be slow when assessed with standard methods, some participants report worsening visual function despite stable visual acuity measures. Functional evaluation of participants with MacTel using fundus-controlled perimetry (microperimetry) reveals characteristic small, deep, paracentral scotomata; these do not necessarily affect performance on single optotype visual acuity testing,⁵ but may affect reading and other visual tasks that require an intact paracentral visual field. Indeed, more pronounced reading disability than would be expected from distance visual acuity testing alone correlate with such paracentral focal loss of macular sensitivity⁶. Moreover, longitudinal data from a recent interventional study showed progressive paracentral visual function loss in a subset of participants while visual acuity remained stable^{7, 26}.

Currently there is no known therapy for MacTel. Previous clinical experience with the NT-501 device in human participants suggests that the device is generally well tolerated. Importantly, the device can be readily removed with a simple procedure. Data from a significant number of human participants also suggest that the risks associated with NT-501 are limited to those expected with the surgical procedure. The use of a sham procedure

in the control participants is justified by the fact that potential bias of the placebo effect could invalidate the study results if a sham arm was not used.

While the placebo impact on the primary endpoint is minimized by the central masked reading of the area of the EZ break, the lack of a sham procedure could very well impact the outcome of the subjective endpoints of visual acuity, reading speed, and vision-related quality of life. The risks of the sham procedure are considered minimal and are clearly outlined in the informed consent form (ICF).

14.1 COMPLIANCE

This study will be conducted in compliance with the protocol, ICH guideline E6: GCP: Consolidated Guideline, and the applicable regulatory requirements from the US CFR, including but not limited to 45 CFR 46 (Human Subjects Protection), 21 CFR 312 (Investigational New Drug [IND]), and 21 CFR 56 (institutional review board [IRB]).

14.2 GOOD CLINICAL PRACTICE

Participant medical information obtained by this study is confidential and may only be disclosed to third parties as permitted by the ICF (or separate authorization to use and disclose personal health information) signed by the participant, or unless permitted or required by law.

Medical information may be given to a participant's physician or other appropriate medical personnel responsible for the participant's welfare for treatment purposes. All active physician investigators are required to be experienced in the conduct of clinical trials and ophthalmologists with training in retinal surgery or retinal medicine. All physician investigators are trained specifically on the procedure for insertion of the device (or the sham procedure) and the handling of the investigational product.

Data generated by this study must be available for inspection upon request by representatives of the US FDA and other regulatory agencies, national and local health authorities, sponsor representatives, and the IRB/IEC for each site, if appropriate.

14.3 DATA AND SAFETY MONITORING COMMITTEE

An independent DSMC will operate according to the DSMC charter that will specify operations, roles and responsibilities, and communication with the sponsor. The committee will meet based on a timeline defined in the DSMC charter until completion of the study.

14.4 STEERING COMMITTEE

A steering committee composed of external experts and study personnel (sponsor and CRO) has been convened to design the protocol and oversee the execution of the study. The steering committee is accountable for ophthalmic medical and technical input and for advising on study execution.

14.5 INFORMED CONSENT

All participants will receive a verbal explanation from the principal investigator or his/her appropriate designee in terms suited to their comprehension of the purposes, procedures, and potential risks of the study. In the opinion of the principal investigator or designee, the participants must be capable of comprehending the contents of the informed consent and able to sign an ICF, which must be obtained prior to enrollment. The participants will have an opportunity to review the ICF carefully and ask questions regarding this study prior to

signing, and they will be informed that they may withdraw from the study at any time without prejudice to themselves.

A template ICF will be provided to each site. The sponsor, or their designee, must review and approve any proposed deviations from the provided ICF template or any alternate consent forms proposed by the site (collectively, the “consent forms”) before IRB/IEC submission. Participants must be re-consented per IRB/IEC requirements with the most current (updated) version of the respective consent form as applicable during their participation in the study. The final IRB/IEC-approved consent forms must be provided to the sponsor for regulatory purposes.

The consent forms must be dated and signed by the person obtaining consent and by the participant before his or her participation in the study. The case history for each participant shall document the informed consent process and that written informed consent was obtained prior to participation in the study. A copy of each signed consent form must be provided to the participant.

All signed and dated ICFs must remain in each participant’s study file and must be available for verification by clinical research associates (CRAs) at any time.

The ICF should be revised whenever there are changes to the procedures outlined in the ICF or when new information becomes available that may affect the willingness of the participant to participate.

For any updated or revised ICFs, the case history for each participant shall document the informed consent process and that written informed consent was obtained for the updated/revised ICF for continued participation in the study. The final revised IRB/IEC-approved ICF must be provided to the sponsor for regulatory purposes.

15. AUDITING AND MONITORING

This study will be conducted in accordance with GCP, using the guidance documents and practices offered by ICH and FDA, and in accordance with the Declaration of Helsinki. This study will also comply with the regulations 21 CFR parts 50, 54, 56, and 312 under an IND application authorized by FDA.

15.1 COMMUNICATION WITH THE INSTITUTIONAL REVIEW BOARD OR INDEPENDENT ETHICS COMMITTEE

This protocol, the ICFs, any information to be given to the participant and relevant supporting information must be submitted to the IRB/IEC by the principal investigator at each site for review and approval before the study is initiated. In addition, any participant recruitment materials must be approved by the IRB/IEC.

The principal investigator is responsible for providing written summaries of the status of the study to the IRB/IEC annually or more frequently in accordance with the regulatory requirements and policies and procedures established by the IRB/IEC. Investigators are also responsible for promptly informing the IRB/IEC of any protocol changes or amendments and of any unanticipated problems involving risk to human participants or others.

In addition to the requirements to report protocol-defined AEs to the sponsor, investigators are required to promptly report to their respective IRB/IEC all unanticipated problems involving risk to human participants. Some IRBs/IECs may want prompt notification of all SAEs, whereas others require notification only about events that are serious, assessed to be related to study treatments, and are unexpected. Investigators may receive written IND safety reports or other safety-related communications from the sponsor. Investigators are responsible for ensuring that such reports are reviewed and processed in accordance with regulatory

requirements and with the policies and procedures established by their IRB/IEC and archived in the site's study file.

15.2 STUDY MONITORING REQUIREMENTS

To ensure compliance with GCP and all applicable regulatory requirements, the sponsor or their representative may conduct a quality assurance audit of the site records, and the regulatory agencies may conduct a regulatory inspection at any time during or after completion of the study. In the event of an audit or inspection, the principal investigator (and institution) must agree to grant the monitor(s) and inspector(s) direct access to all relevant documents and to allocate their time and the time of their personnel to discuss any findings/relevant issues. The principal investigator will permit the monitors, sponsor representatives, US FDA, other regulatory agencies, IRBs, and the respective national or local health authorities to inspect facilities and records relevant to this study.

15.3 RECORDS MANAGEMENT

The investigator will permit study-related monitoring, audits, and inspections by the IRB/IEC, the sponsor, government regulatory bodies, and compliance and quality assurance groups of all study-related documents (eg, source documents, regulatory documents, data collection instruments, study data). The investigator will ensure the capability for inspections of applicable study-related facilities (eg, pharmacy, diagnostic laboratory). All authorized personnel, including health authority inspector(s), sponsor and designees, monitor(s), and auditor(s) will be given direct access to source data and documentation (eg, medical records, laboratory results) for source data verification, provided that participant confidentiality is maintained in accordance with local requirements.

The unmasked staff at the CRO will maintain the randomization codes and procedures.

15.4 DATA QUALITY ASSURANCE

The CRO will have the primary responsibility for assuring that the data collected and reported in the study are of consistently high quality. Many factors contribute to the quality of the data, from the design and procedures of the trial to the analytic methods employed.

The major quality assurance features of the study are as follows:

- Standard data collection forms and procedures
- Common protocol for eligibility, examination, and follow-up of all participants at all sites
- Masked assessment of the primary outcome measure and secondary outcome measures
- Central masked grading of study images
- Data entry into EDC
- Central, computer driven data editing for missing, invalid, and suspect responses
- Regular reporting of performance of all sites
- Monitoring visits to all sites
- Certification of clinic personnel and of imaging equipment

15.5 SOURCE DOCUMENTATION

All data relating to study procedures will be entered by trained site personnel into the electronic case report form (eCRF) around the time of study assessment collection. The eCRF exists within an EDC system with controlled access managed by the sponsor or its designee for this study. Study personnel will be appropriately trained in the use of eCRFs before the start of the study and prior to being given access to the EDC system. Original data and any changes to data will be recorded using the EDC system, with all changes tracked by the system and recorded in an electronic audit trail.

All eCRFs should be completed by designated, trained examining personnel, or the study coordinator as appropriate.

The investigator will attest that the information contained in the eCRFs is true by providing electronic signature within the EDC system prior to database lock. After database lock, the investigator will receive a copy of the participant data for archiving at the site. At all times, the investigator has final responsibility for the accuracy and authenticity of all clinical data.

The CRAs will perform ongoing site visits to confirm that critical protocol data (ie, source data) entered into the eCRFs by authorized site personnel are accurate, complete, and verifiable from source documents.

Source documents are where participant data are recorded and documented for the first time. They include, but are not limited to, hospital records, clinical and office charts, memoranda, evaluation checklists, recorded data from automated instruments, copies of transcriptions that are certified after verification as being accurate and complete, photographic negatives, magnetic media, and medico-technical departments involved in the clinical trial.

To facilitate monitoring, the investigator(s) and institution(s) must provide the sponsor direct access to applicable source documents and reports for trial-related monitoring, sponsor audits and IRB/IEC review. The site must also allow inspection by applicable regulatory authorities.

When clinical observations are entered directly into the site's computerized medical record system (ie, in lieu of original hardcopy records), the electronic record can serve as the source document if the system has been validated in accordance with FDA requirements pertaining to computerized systems used in clinical research. An acceptable computerized data collection system (for clinical research purposes) would be one that (1) allows data entry only by authorized individuals, (2) prevents the deletion or alteration of previously entered data and provides an audit trail for such data changes (eg, modifications of file), (3) protects the database from tampering and (4) ensures data preservation.

If a site's computerized medical record system is not adequately validated for the purposes of clinical research (as opposed to general clinical practice), applicable hardcopy source documents must be maintained to ensure that critical protocol data entered into the eCRFs can be verified.

15.6 STUDY FILES AND RECORD RETENTION

The US FDA regulations (21 CFR §312.62[c]) and ICH Guideline for GCP (see Section 4.9 of the guideline) require that records and documents pertaining to the conduct of this study, including eCRFs and ICFs, must be retained by the principal investigator for 2 years after the last marketing application approval in an ICH region or after at least 2 years have elapsed since formal discontinuation of clinical development of the investigational product. All state and local laws for retention of records also apply.

No records should be disposed of without the written approval of the sponsor. Written notification should be provided to the sponsor for transfer of any records to another party or moving them to another location.

For studies conducted outside the US under a US IND/IDE, the principal investigator must comply with the record retention requirements set forth in the US FDA IND/IDE regulations and the relevant national and local health authorities.

16. AMENDMENTS

Protocol modifications, except those intended to reduce immediate risk to study participants, may only be made by the sponsor. A protocol change intended to eliminate an apparent immediate hazard to participants may be implemented immediately, provided the IRB/IEC is notified within 5 days.

Any permanent change to the protocol must be handled as a protocol amendment. The written amendment must be submitted to the IRB/IEC and the investigator must await approval before implementing the changes. The sponsor or their designee will submit protocol amendments to the appropriate regulatory authorities for approval.

If in the judgment of the IRB/IEC, the investigator, and/or the sponsor, the amendment to the protocol substantially changes the study design and/or increases the potential risk to the participants, and/or has an impact on the participants' involvement in the trial, the currently approved written ICF will require similar modification. In such cases, informed consent will be renewed for participants enrolled in the study and the new ICF signed before continued participation.

17. STUDY REPORT AND PUBLICATIONS

The sponsor or their designee is responsible for preparing and providing the appropriate regulatory authorities with clinical study reports according to the applicable regulatory requirements. The publication policy of the sponsor is discussed in the investigator's clinical research agreement.

18. STUDY DISCONTINUATION

Both the sponsor and the principal investigator reserve the right to terminate the study at the investigator's site at any time. Should this be necessary, the sponsor or a specified designee will inform the appropriate regulatory authorities of the termination of the study and the reasons for its termination, and the principal investigator will inform the IRB/IEC of the same. If the decision is made to terminate the study, the sponsor and the principal investigator will assure that adequate consideration is given to the protection of the participants' interests.

The investigator may discontinue a participant from the study if warranted. The investigator and the sponsor may also request the withdrawal of a participant because of noncompliance (eg, missed visits), administrative reasons, or any other valid and ethical reasons.

Reasons for participant discontinuation may include, but are not limited to, the following:

- Investigator determination that it is not in the best interest of the participant to continue participation
- Intercurrent illness
- AE that is serious and unexpected
- Worsening condition
- Any other safety concerns

If a participant withdraws or is discontinued from the study before the Month-24 Visit, they should return for an exit visit. The schedule of assessments for this visit is the same as that for the 24 month.

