5.6 MASKING

There are different levels of masking within the study. The participant is masked to treatment assignment throughout the study. The refractionist, visual acuity examiner, and photographers/imagers must be masked to treatment assignment (implant or sham procedure) for all follow-up visits. The ophthalmologist, surgeon, and clinic coordinator will be unmasked to treatment assignment. To ensure that the participant remains masked to the randomized assignment, the ophthalmologist, surgeon, and clinic coordinator are to not discuss the treatment received with the participant. All personnel at the image reading center will be masked to whether the participant received the implant or sham in the study eye.

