The safety population will include the data from all randomized participants who receive any treatment and have at least 1 safety measurement. Participants will be analyzed in the group according to the treatment received, and no subjects (or data) will be excluded from this dataset because of protocol violations that occur during the study.

The efficacy analysis will be conducted on the mITT population and on the PP population. Safety analyses will be performed using the safety population. The handling of participants with missed visits or visits occurring outside the specified windows will be considered in the SAP.

If both eyes of a participant qualify for the study, the study eye will be selected using the centralized randomization process.

Continuous variables will be summarized using descriptive statistics (n, mean, standard deviation [SD], median, minimum, and maximum), and categorical variables will be summarized using the count and percentage of participants in each category.

Significance Level:

A significance level, α , of 0.05 will be used for statistical testing of the primary and secondary endpoints.

A hierarchical testing procedure will be applied to secondary efficacy analyses to control the overall type I error rate. In the case that the primary efficacy analysis is statistically significant at a 2-sided type I error rate of 0.05, the secondary efficacy endpoints will be tested at a 2-sided type I error rate of 0.05 in the order listed below. If any of the secondary endpoints are found to be not statistically significant at the 2-sided 0.05 level, the hypothesis testing will stop. Later endpoint(s) after a non-statistically significant result will be summarized descriptively and p-values may be produced for descriptive purposes only.

- Mean change in aggregate sensitivity of microperimetry within the EZ line break area from the Baseline Visit through the Month 24 Visit
- Mean change in reading speed from the Baseline Visit through the Month 24 Visit
- Mean change in the National Eye Institute Visual Function Questionnaire-25 (NEI-VFQ-25) near activities subscale score from the Baseline Visit through the Month 24 Visit

Accounting for Missing Data:

Every attempt will be made to collect data per the protocol and to avoid missing data. As such, dropouts and missing data are expected to be minimal, but can inevitably occur. For cases with unavoidable missing data, no imputation will occur.

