18.1 PREMATURE DISCONTINUATION

Premature discontinuation is not anticipated to be a frequent event based on the history of previous clinical trials with this device. The investigator may discontinue a participant from the study if warranted and only after discussion with the medical monitor. If the participant discontinues study participation before completing the defined 24, 36 or 48 months of follow-up, the principal investigator and study coordinator of the study site for the NHOR will be notified to ensure long-term follow-up.

If a participant requests explanation and withdrawal from the study, this can be readily arranged. The investigator should contact the sponsor's medical monitor to discuss the reasons for the request and discuss the procedure for explanation. If a participant discontinues from the study they will not be replaced once recruitment is complete.

If a participant requests explanation but does not wish to withdraw from the study, this is also acceptable. The participant would continue in the study with all planned follow-up visits and assessments. For COVID-related out of window visits conducted less than 119 days beyond the protocol specified visit, an estimated value for the scheduled visit will be computed from the raw data and time using the actual out of window visit date, computed as month from surgery.

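### Protocol Section 18 does not separate discontinuation from the end of data collection, so unmasked investigators can end follow-up for reasons tied to the outcome

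*Protocol*

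**What the plan says.** **Discontinuation.** Protocol Section 18 states: "The investigator may discontinue a participant from the study if warranted". Its non-exhaustive list of reasons includes "Worsening condition", with no definition or threshold, and a serious, unexpected adverse event. Of investigator and sponsor alike, it says that they "may also request the withdrawal of a participant because of noncompliance (eg, missed visits), administrative reasons, or any other valid and ethical reasons". A participant who leaves before Month 24 should return for an exit visit with the Month-24 assessments, which include SD-OCT (Section 7.2.11).

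**Who decides.** Protocol 5.6: "The ophthalmologist, surgeon, and clinic coordinator will be unmasked to treatment assignment". Protocol 14.2 requires active physician investigators to be "ophthalmologists with training in retinal surgery or retinal medicine". Read together, the person who may discontinue a participant belongs to the unmasked group.

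**Treatment and follow-up.** The device is implanted once (Protocol 1.2.8). For someone who asks for explantation but does not wish to withdraw, Section 18.1 says: "The participant would continue in the study with all planned follow-up visits and assessments". Section 18.1 also requires discussion with the medical monitor before the investigator discontinues anyone, and notice to the registry (NHOR) site when a participant leaves early.

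**Analysis.** Protocol 12.3.1 and SAP 9.1 restrict the primary analysis to participants with Baseline, Month 24 and at least one of Months 12, 16 or 20. SAP 9.2 compares the secondary endpoints on observed Baseline and Month-24 values without imputation. SAP 8.1 plans a Kaplan-Meier comparison of premature discontinuation. SAP 9.1.1 plans a sensitivity analysis of all observed assessments.

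**The concern.** In a progressive disease measured by lesion growth, getting worse is close to the endpoint itself. Section 18 makes no distinction between stopping for a clinical or administrative reason and ending measurement. A site acting within the text could therefore stop imaging participants who are doing badly, or who have had a device event, while knowing their arm. Central masked reading protects the grading of a scan. It does not protect the decision on whether another scan is taken.

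Such loss can push the slope comparison either way. Losing fast progressors from sham hides a benefit, and losing them from NT-501 exaggerates one. The same participants would have no Month-24 reading speed, NEI-VFQ-25 or microperimetry value. Safety data are cut short too: after premature withdrawal, adverse events are followed only to 30 days after the last visit (Protocol 10.4), whereas the SAP's safety endpoints run through Month 24 (SAP 3.2.2.2).

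**Working it through.** **1. The plan's own figure.** Inputs from Protocol 12.2 and SAP 5: two-sided α = 0.05, power 80%, σ² = 0.0256, ρ = 0.6, n = 5, s²ₓ = 0.47, d = 0.037 mm²/yr.

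m = 2(1.960 + 0.842)² × 0.0256 × (1 − 0.6) / (5 × 0.47 × 0.037²) = 49.97, so 50 per arm. This reproduces. Raising 50 to 56 leaves room for 6/56 = 10.7% loss per arm. By the same formula, power with all 56 followed is 84.3%. The margin protects power, not against selective loss.

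**2. What happens to a participant withdrawn at, say, Month 16.** The exit visit yields a scan. Neither document says that an early exit visit counts as Month 24, so on the text as written the participant fails the three-visit restriction and leaves the primary analysis, earlier scans included. The all-observed sensitivity analysis recovers scans already taken but is not primary. Neither document brings registry data into the trial analysis.

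**3. Worst-case illustration.** Assumptions, not in the documents: true slopes are normal within arm with SD τ = 0.05 to 0.15 mm²/yr, and exactly the fastest fraction f of one arm is lost. The mean of the top fraction lies φ(z)/f SDs above the arm mean, so the mean of those remaining falls by [f/(1 − f)] × [φ(z)/f] × τ.

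| f | φ(z)/f | Fall, τ = 0.05 | Fall, τ = 0.15 | Share of 0.037 |
|---|---|---|---|---|
| 2.5% | 2.34 | 0.0030 | 0.0090 | 8 to 24% |
| 5% (about 3 of 56) | 2.06 | 0.0054 | 0.0163 | 15 to 44% |
| 10% | 1.75 | 0.0097 | 0.0292 | 26 to 79% |

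**4. Simulation with selection on observed change.** There were 3,000 runs per scenario with 56 per arm, the plan's variance and correlation, and a sham slope of 0.270/2 = 0.135 mm²/yr (Phase 2, Protocol 1.1). Participants with the largest change from Baseline to Month 16 in one arm are lost and then dropped for lack of Month 24. With no slope variation between participants:

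- No true effect, 6 of 56 lost from NT-501: the estimate shifts by 0.0084 mm²/yr (0.0084/0.037 = 23%), and the chance of a false win for NT-501 is 10.5% against a nominal 2.5%.
- The same with 3 of 56 lost: shift 0.0046, false-win chance 5.7%.
- True difference 0.037, 6 of 56 lost from sham: the estimate falls to 0.028 and power from about 84% to 61%.
- Six lost from each arm: no shift.

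With an assumed slope SD of 0.05 or 0.10, losing 6 of 56 from NT-501 under no effect gives shifts of 0.0116 and 0.0197.

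**5. How much comes from the completer restriction.** In the same NT-501 scenarios, keeping the lost participants' data up to Month 16 in the random-intercept model leaves a shift of 0.0003 with no slope variation, 0.0027 at slope SD 0.05 and 0.0088 at 0.10. Against step 4, that removes nearly all of it, 1 − 0.0027/0.0116 = 77%, and 1 − 0.0088/0.0197 = 55%. Only later scans can address the remainder.

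**The case against.** **Safeguards are in place.** They include discussion with the medical monitor, an exit visit with full assessments, registry notice, a Kaplan-Meier comparison and an all-observed sensitivity analysis. This stands as mitigation. Discussion is not approval, however, and the text sets no criterion for it. The Kaplan-Meier comparison may reveal an imbalance but cannot correct one.

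**The clause is permissive and may not mean MacTel.** The phrase sits among intercurrent illness and safety concerns, so general health is a natural reading. That is fair, but being undefined it covers both readings, and both allow outcome-related loss. For missed visits the text only allows withdrawal to be requested.

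**Premature discontinuation is expected to be infrequent** (Protocol 18.1), and the illustrations assume one-sided selection. This also stands. Nothing in the documents supports 5 to 10% of one arm leaving for worsening, and investigators do not observe true slopes.

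**Stronger readings the documents do not support.**

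- A reader might infer that lost information is beyond any analysis. Step 5 shows that data observed before exit recover much of it.
- A reader might class the exit visit as an unscheduled measurement under SAP 7.1. Section 18 prescribes that visit, and the SAP never classifies it. The documents are silent.
- A reader might see a contradiction with Protocol 12.1: "Every attempt will be made to collect data per the protocol and to avoid missing data". The same section accepts that some missing data will occur. The two provisions pull in different directions without contradicting each other.

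**Conclusion.** The gap is real and lies in the wording: discontinuation for the listed reasons is not separated from the end of measurement, the decision-maker is unmasked, and the primary analysis then drops the participant. The documents do not show that the clause has been used selectively or that the result is biased, and a reader should not infer either.

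The 0.005 to 0.016 mm²/yr shift (15 to 44% of 0.037) for 5% lost from one arm is a worst case. It rests on an assumed slope SD of 0.05 to 0.15, perfect selection and loss in one arm only. Part of any such effect comes from the completer restriction rather than from Section 18. The wording is certain and the size is not. A clarification is worthwhile because it is cheap and uses visits already scheduled.

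Nor does the point support removing the adverse-event or other safety-related reasons from Section 18. Those protect participants, and the statistical need is met without touching them.

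**What to change.** Keep the listed reasons and all clinical discretion. Two additions are needed:

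1. **Protocol Section 18.** State that worsening condition, an adverse event, missed visits or explantation do not by themselves end data collection. Participants who still consent and are able to attend stay on the scheduled assessments, including SD-OCT, through Month 24. This extends what Section 18.1 already allows after explantation.
2. **Protocol 12.3.1 and SAP 9.1.** State that observed data from participants who leave early, including the exit visit at its actual study day, enter the primary mixed model. This fits the continuous study-day model and SAP 7.1, which says the mixed model uses all available data. If the categorical-time fallback in SAP 7.6 is adopted, the SAP should also say how an early exit visit is placed.

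**Cost.** A protocol amendment with IRB/IEC approval and possibly a consent update (Protocol 16), and a SAP amendment before database lock. A few participants would attend visits already in the schedule. Protocol 4.1 provides for Month-24 visits after 01 December 2021, so at the date of this protocol version the change could still prevent loss.
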